	24.4 Essential documents and retention of documents	26
	24.5 Maintenance of data confidentiality	26
	24.6 Reports	26
	24.7 Risk management	27
app	pendix	28
refe	ferences	29

ABSTRACT

Objectives	To assess the efficacy of ertugliflozin on reduction of functional mitral
	regurgitation after 12 months of treatment
Study Design	Multicenter, randomized, double-blind, placebo-controlled trial
Study Subjects	Patients with left ventricular dysfunction and secondary functional mitral regurgitation of stage B and C
Treatment arms	 Ertugliflozin Placebo
Sample Size	128 subjects
Duration	12 months following randomization
Participating	Asan Medical Center, Seoul National University Hospital,
Center	Samsung Medical Center, Seoul National University Bundang Hostpital, Severance Hospital, Inha University Hospital
Primary Endpoint	Change of effective regurgitant orifice area (EROA) of functional mitral regurgitation from baseline to 12 months follow-up
	Change of regurgitant volume from baseline to 12 months follow-up
	Change of left ventricular end-systolic volume from baseline to 12 months follow-up
Secondary Endpoints	Change of left ventricular end-diastolic volume from baseline to 12 months follow-up
Znaponits	Change of NT-proBNP (N-terminal of the prohormone brain natriuretic peptide) from baseline to 12 months follow-up
	Change of left atrial volume index from baseline to 12 months follow-up

1 Title and phase of trial

6.1 Study Purpose

The primary objective of the EFFORT trial is to assess the efficacy of ertugliflozin on reduction of functional mitral regurgitation (MR) after 12 months of treatment. The secondary objective is to examine whether ertugliflozin is effective in reversing left ventricular remodeling (LV) and to evaluate whether reduction of MR and reversal LV remodeling by ertugliflozin improves cardiovascular outcomes.

6.2 Background

In patients with heart failure (HF) and LV dilation, adverse LV remodeling causes tethering of mitral valve (MV) preventing sufficient coaptation of normal leaflets and resulting in functional MR (1-4). Because secondary functional MR usually develops as a result of LV dysfunction, guideline-directed medical therapy for HF forms the mainstay of therapy (5). However, beta blockers, angiotensin-converting-enzyme (ACE) inhibitors, and angiotensin receptor blockers (ARB) fail to reverse adverse LV remodeling and functional MR (6-7), and the morbidity and mortality of patients with functional MR remain high despite standard medical therapy (8-10).

A recent randomized trial (11) (GW Stone et al. COAPT trial. NEJM 2018) proved that reduction of functional MR by transcatheter MV repair resulted in a lower rate of hospitalization for HF and lower mortality in patients with HF and significant secondary MR, and we recently demonstrated that the angiotensin receptor-neprilysin inhibitor (ARNI) is more effective in improving functional MR associated with HF than the ARB in a double-blind, randomized trial (12) (Kang et al. Circulation. 2019 Mar). In our trial, we enrolled 118 stable HF patients with functional MR, whose effective regurgitant orifice area (EROA) larger than 0.1 cm², lasting > 6 months despite standard medical treatment, and the primary end point of change in EROA was significantly different between the ARNI group and the ARB group (-0.058±0.095 versus -0.018±0.105 cm²; P=0.032), and a decrease in end-diastolic volume index of the LV was also significantly greater in the ARNI group than in the ARB group (P=0.044).

6.3 Result of precedent study

Sodium-glucose co-transporter-2 (SGLT2) inhibitors reduce cardiac preload and afterload by natriuresis and lowering arterial stiffness, similar to the neprilysin inhibitor that facilitates sodium excretion and has vasodilating effects (13-16). In addition, effects on blood pressure reduction and weight loss may ultimately have a beneficial effect on LV remodeling. Recently it has been reported that SGLT2 inhibitors have a multifaceted effect on cardiac function including improvement in endothelial dysfunction and aortic stiffness (17), reduction in epicardial fat accumulation (18) as well as in visceral adipocyte hypertrophy (19).

In a prospective multicenter trial of 58 type 2 diabetes patients with stable HF in Japan, LV mass index (31 to

26 mL/m², p=0.001) and LA volume index (75.0 to 67.0 g/m², p <0.001) were significantly reduced 6 months

after the administration of dapagliflozin (20). There were also significant decreases in markers of LA and LV

end-diastolic pressures such as E/e' (9.3 to 8.5 cm/s, p=0.020) and BNP (168.8 to 114.3 pg/mL, p=0.012) in

patients with baseline BNP ≥ 100 pg/mL. This association between SGLT2 inhibitors and improvements of

LV diastolic function and LV remodeling has been reported in other SGLT2 inhibitors (21, 22). In our previous

trial with ARNI (12), we also found significant differences in changes in LA volume index, LV end-diastolic

volume index and E/e', and association between changes in these parameters and improvement of functional

MR. With these results, SGLT2 inhibitor is expected to have a favorable effect on LV and LA remodeling, and

improve cardiovascular (CV) outcomes by decreasing functional MR.

A few randomized trials (23-27) to explore CV benefit of the SGLT2 inhibitor have been performed and

showed a significant reduction on the risk of CV death or hospitalization for HF. However, its effect on cardiac

structure and function was not evaluated and further mechanistic studies are needed to interpret beneficial

clinical effects of the SGLT2 inhibitors. Based on studies demonstrating SGLT2 inhibitors' favorable effects

on LV and LA modeling, we hypothesize that SGLT2 inhibitor, ertugliflozin, is effective on improving MR in

patients with functional MR secondary to LV dysfunction and try to examine this hypothesis in a multicenter,

double-blind, randomized comparison study using echocardiography.

7 Name and characteristics of drugs

1) Study drug and matching placebo

1 Trade name: Steglatro

2 Generic name: Ertugliflozin

3 Appearance

5 mg: pink color, triangular shape and film coated tablet

4 Drug contains: same as approval

8 **Study indication**

Patients with left ventricular dysfunction and secondary functional and ischemic mitral regurgitation

7

9 Inclusion / exclusion criteria and study population

9.1 Inclusion Criteria

To be included, patients must fulfill ALL of the following:

Inclu	Inclusion Criteria:				
1.	Patients must agree to the study protocol and provide written informed consent				
2.	Outpatients ≥ 20 years of age, male or female				
3.	Non-diabetic or type2 DM patients with HbA1c 7.0-10.5%				
4.	Patients with secondary functional MR (stage B and C) and LV dysfunction				
	Symptoms due to coronary ischemia or heart failure may be present but symptoms due				
	to MR should be absent				
	Normal mitral valve leaflets and chords				
	Regional or global wall motion abnormalities with mild or severe tethering of leaflet				
	• MR whose ERO > 0.10 cm ² and which lasted > 6 months under medical treatment with				
	a β-blocker and an ACE inhibitor (or ARB)				
	• 35% < LV ejection fraction < 50%				
5.	Dyspnea of NYHA functional class II or III				
6.	Titration of HF medications should be completed and patients must take a stable, optimized dose of a				
	β-blocker and an ACE inhibitor (or ARB) for at least 4 weeks prior to study entry				

9.2 Exclusion Criteria

Exclu	Exclusion Criteria				
1.	History of hypersensitivity or allergy to the study drug, drugs of similar chemical classes, or SGLT-2				
	as well as known or suspected contraindications to the study drug				
2.	Current use or prior use of a SGLT-2 inhibitor or combined SGLT-1 and 2 inhibitor				
3.	Known history of angioedema				
4.	Any evidence of structural mitral valve disease, including prolapse of mitral leaflets and rupture of				
	chords or papillary muscles				
5.	Current acute decompensated heart failure or dyspnea of NYHA functional class IV				
6.	Medical history of hospitalization within 6 weeks				

7.	Symptomatic hypotension and/or a SBP < 100 mmHg at screening			
8.	Estimated GFR < 45 mL/min/1.73m ²			
9.	History of ketoacidosis			
10.	Evidence of hepatic disease as determined by any one of the following: AST or ALT values exceeding			
	2 x upper limit of normal (ULN) at screening visit (Visit 0), history of hepatic encephalopathy, history			
	of esophageal varices, or history of portacaval shunt.			
11.	Acute coronary syndrome, stroke, major CV surgery, PCI within 3 months			
12.	Substantial myocardial ischemia requiring coronary revascularization, a plan of coronary			
	revascularization or mitral valve intervention within 1 year			
13.	Indication of cardiac resynchronization therapy, a plan of heart transplantation or implantation of			
	cardiac resynchronization therapy			
14.	History of severe pulmonary disease			
15.	Significant aortic valve disease			
16.	Women of child-bearing potential, defined as all women physiologically capable of becoming			
	pregnant, unless they are using a barrier method plus a hormonal method			
17.	Pregnant or nursing (lactating) women			
18.	Any clinically significant abnormality identified at the screening visit, physical examination, laboratory			
	tests, or electrocardiogram which, in the judgment of the investigator, would preclude safe completion			
	of the study			
19.	History of galactose intolerance, Lapp lactase deficiency, or glucose-galactose malabsorption			

9.3 Sample size calculation and basis of sizing

9.3.1 Target subject number: 224

9.3.2 Basis of calculation

We would like to have 90% power to detect a 0.05 cm² difference in EROA at 12 months between ertugliflozin and placebo group. Using a two-sided t-test with an alpha level of 0.05, sample size of 204 or 102 patients per treatment arm is required. In our previous trial (Kang DH, et al. Angiotensin receptor neprilysin inhibitor for functional mitral regurgitation, Circulation 2019;139:1354-1365), change in effective regurgitant orifice area was significantly greater in the ARNI group than the ARB group (-0.058 ± 0.095 versus -0.018 ± 0.105 cm2; P=0.032) and difference in change between the two groups was 0.040 ± 0.019 . Based on our previous trial, we assume that a common baseline mean value is 0.21 cm² and a common SD of the change from baseline is 0.11

cm² in both groups, and SD of the difference in change between the two groups is 0.019 cm². Assuming a dropout rate of 10%, the target number of patients to be randomized is 224.

COVID-19 pandemic seriously affected enrollment of study patients. Although the rate of patient recruitment was much lower than expected, the sponsor made a decision to adhere to the original study timeline and provide new study drug no longer in 2022. According to expiration date of supplied study drug, the Executive Committee decided to stop enrollment in December 2022 without knowledge of any trial data and the actual number of study patients was 128, smaller than the target sample size of 224 patients. Although the smaller actual sample size may result in an underpowered study to provide the hazard ratio, this trial is still expected to show significant differences in primary or secondary endpoints with careful assessment of outcomes and follow-up of all study patients.

10 Study timeline

On the basis of a lower than expected rate of patient recruitment and a limited supply of study drug, the Executive Committee finished enrollment in December 2022 without knowledge of any trial data. Overall study will require 38 months to complete, including 26 months of recruitment and 12 months of follow up and close out

- First patient in: November 2020
- Last patient in: December 2022
- Last patient out: December 2023
- First results available: March 2024

11 Trial Design

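### Section 9.3.2 gives 90% power for 204 evaluable patients only; at the final 128 it is about 72% at the plan's SD (68% to 84% over the quoted SDs and 0–10% dropout), and the only underpowering caveat names a hazard ratio that no endpoint defines

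*Combined protocol and SAP*

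**What the plan says.** Section 9.3.1 still reads "Target subject number: 224". Section 9.3.2 gives the basis: "We would like to have 90% power to detect a 0.05" cm² difference in EROA at 12 months, by a two-sided t test at alpha 0.05, so that a "sample size of 204 or 102 patients per treatment arm is required". The planning SD is stated as "a common SD of the change from baseline is 0.11" cm². Allowing for 10% dropout takes the number to 224.

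The next paragraph of 9.3.2 reports that recruitment and drug supply fell short and that "the actual number of study patients was 128, smaller than the target sample size of 224 patients". It then makes two statements in one sentence:

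- the caveat: "the smaller actual sample size may result in an underpowered study to provide the hazard ratio";
- the reassurance: the trial is "still expected to show significant differences in primary or secondary endpoints with careful assessment of outcomes and follow-up of all study patients".

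Neither statement carries a figure. The primary endpoint (16.1.1) is the change in EROA. The six secondary endpoints (16.1.2) are also changes from baseline to 12 months. Section 16.3 tests the primary hypothesis with a t test or, if the data are not normal, a Mann-Whitney U test. Section 6.1 includes among the secondary aims "to evaluate whether reduction of MR and reversal LV remodeling by ertugliflozin improves cardiovascular outcomes", but no time-to-event endpoint or analysis follows from it.

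**The concern.** The only power figure in the plan belongs to a trial of 204 evaluable patients, and the trial now has 128 randomised. The text admits a loss of power but attaches it to a hazard ratio, which nothing in the plan would estimate. For EROA, where the loss actually falls, the same sentence says that significance is still expected.

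What is at stake is how a non-significant EROA result is read. Someone who takes 9.3.2 at face value sees 90% power and a warning about something else, and could treat a null result as stronger evidence of no effect than the design supports.

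**Working it through.** **Inputs.** All come from 9.3.2 unless noted.

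- Difference 0.05 cm²; two-sided alpha 0.05; t test.
- Planning SD of change 0.11 cm². SDs of change in the investigators' previous trial: 0.095 and 0.105 cm², which pool with equal weights to √((0.095² + 0.105²)/2) = 0.100.
- 128 randomised 1:1 (11.3.1), taken as 64 per arm.
- Dropout: none, or the plan's 10% carried over from the 224 target. The latter is an assumption: 128 × 0.9 = 115.2, taken as 58 + 57.

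The 0.019 cm² that 9.3.2 calls an SD of the difference between groups is left out. It behaves like a standard error: √((0.095² + 0.105²)/59) = 0.018, assuming that the previous trial's 118 patients split evenly.

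**Step 1: reproduce the plan.** By the normal approximation,

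n per arm = 2 × [(1.960 + 1.2816) × 0.11 / 0.05]² = 101.7, so 102 per arm and 204 in total.

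This matches. Noncentral-t power at 102 per arm is 89.8%. For dropout, 204 × 1.10 = 224.4 matches the stated 224.

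**Step 2: power at the final size.** The noncentrality is 0.05 / [SD × √(1/n₁ + 1/n₂)] on n₁ + n₂ − 2 degrees of freedom. At SD 0.11 and 64 per arm the standard error is 0.11 × √(2/64) = 0.01945, the noncentrality is 2.571, the critical t on 126 df is 1.979, and power is 72.3%. The other cases follow in the same way:

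| SD of change (cm²) | 64 per arm | 61 per arm (5% dropout) | 58 + 57 (10% dropout) |
|---|---|---|---|
| 0.11 (plan) | 72% | 70% | 68% |
| 0.105 | 76% | 74% | 72% |
| 0.10 (pooled) | 80% | 78% | 76% |
| 0.095 | 84% | 82% | 80% |

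**Step 3: what would restore 90%.**

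- The difference detectable with 90% power at SD 0.11 is 0.0635 cm² with 64 per arm and 0.0671 cm² with 58 + 57.
- For 0.05 cm² the SD would have to be 0.087 (64 per arm) or 0.082 (58 + 57). Both lie below either SD quoted from the previous trial.

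**Step 4: sensitivity.**

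- If the Mann-Whitney U test is used on near-normal data (relative efficiency 3/π = 0.955), power at SD 0.11 is about 70%, or 66% with 115 evaluable. For other distributions the documents give no basis for a figure.
- All figures keep the planned 0.05 cm² effect. At the 0.040 cm² observed in the previous trial, power at SD 0.11 with 64 per arm is about 53%.

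**The case against.** The strongest reply is that no stated number is wrong. The calculation reproduces, 90% is expressed as an aim tied to 204 patients, and nothing claims 90% at 128. The shortfall is disclosed with its reason, the word underpowered appears, and the decision to stop was made without knowledge of trial data. A reader can work out 72% from the inputs given. A null result will in any case be judged mainly from the estimate and its confidence interval (half-width about 1.979 × 0.01945 = 0.038 cm² at SD 0.11 with 64 per arm), not from planning power. Enrolment had closed, so a correction changes no conduct or analysis.

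Much of this is fair. There is no concealment, and the 224 in 9.3.1 needs only clarification. But the disclosure covers the patient count, not its consequence for EROA, and the one statement about power names a quantity the trial will not produce.

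The range also needs careful reading. On the plan's own SD it is 68% to 72%. The 84% end applies one arm's SD from the previous trial to both arms with no dropout, and at that SD the original 204 patients would have had about 96%. The low end assumes 10% dropout, whereas sections 9.3.2 and 15 aim for complete follow-up. Complete follow-up removes only the dropout loss, leaving 72% at SD 0.11.

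**Conclusion.** The concern holds. At SD 0.11 and a true difference of 0.05 cm², the chance of a non-significant result rises from 10% in the original plan to 28% with all 128 patients evaluable, or 32% with 10% dropout. Over the SDs of change quoted in 9.3.2 it is 16% to 32%, so power is below 90% throughout.

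These figures assume a two-sided t test at 0.05, an equal split of 128 and the planned effect size. The hazard-ratio caveat is wrong as written, because no endpoint or analysis in section 16 yields one. The expectation of significance has no figure behind it. This should be corrected, although the design itself is not affected.

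**What to change.** - **9.3.1:** state the original target of 224 and the 128 randomised side by side.
- **9.3.2, first paragraph:** label the 90% / 204 / 224 calculation as the original plan.
- **9.3.2, last sentence** (hazard ratio and expected significance): replace it in full with, for example:

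> With 128 patients randomised, power to detect a 0.05 cm² difference in EROA change by two-sided t test at alpha 0.05 is about 72% at SD 0.11 (about 68% if 10% drop out) and about 80% (76%) at SD 0.10. The difference detectable with 90% power at SD 0.11 is about 0.064 cm² (0.067 cm²). The trial is therefore underpowered for its primary endpoint relative to the original plan.

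SD 0.10 is the value pooled from the two quoted SDs and should be identified as such.

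**Cost.** The change is to wording only: no endpoint, test, population, alpha or patient number changes. Under 24.2 it still needs a written amendment with IRB approval. The downside is that the stated power becomes less favourable.

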11.1 Study outline

[figure not shown]
This study is a prospective, multicenter, randomized, double-blind, two arm parallel group, placebo-controlled clinical trial involving patients with LV dysfunction and functional MR. Patients meeting inclusion criteria without any exclusion criteria will be randomized 1:1 to ertugliflozin 5mg or placebo therapy. Randomization will be stratified according to ischemic or non-ischemic cause of functional MR, presence of diabetes mellitus and cardiac rhythm, and the upper limit of randomized non-DM patients will be set as 90 patients (70%). The enrolment period was 26 months (n=128) and all patients will be followed for 12 months after randomization. Endpoints will be measured at 12 months. We design the protocol and conduct the trial in accordance with the principles of the Declaration of Helsinki, and the study protocol will be approved by the institutional review board (IRB).

11.2 Screening and recruiting protocol

The investigator at each clinical center will be responsible for case finding and subject recruitment. Echocardiographic studies performed as part of routine care before enrollment will be reviewed to determine if ERO of functional MR > 0.10 cm² and 35% < LV ejection fraction < 50% (inclusion criterion #4). For the purpose of screening, an echocardiogram performed within 24 months of enrollment, at a study center can be used. All eligible patients should be on standard medications for underlying heart failure (HF), which include an individually optimized dose of a beta-blocker and an ACE inhibitor (or ARB) at a stable dose for at least 4 weeks prior to study entry. After consultation with the patient's cardiologist, potential study participants will be approached about participation. At this time, a final determination about study eligibility will be made, and eligible patients will be asked to participate in the study.

Figure 1. Trial Flow

Primary end point: Change of effective regurgitant orifice area from baseline to 12 months follow-up

Secondary End Point: Change of regurgitant volume, end-systolic volume, end-diastolic volume, LA volume index, N-terminal of the prohormone BNP level, left ventricular global longitudinal strain from baseline to 12 months follow-up

11.3 Treatment

11.3.1 Investigational and Control Drugs

- 128 patients will be randomized at a ratio 1:1 to two arms:
- a) Ertugliflozin
- b) Placebo

All study patients will receive ertugliflozin or placebo in addition to their usual medications. Titration of HF medications should be completed and patients must take a stable, optimized dose of a β -blocker and an ACE inhibitor (or ARB) for at least 4 weeks prior to study entry.

The following doses of study drugs will be provided.

✓ Ertugliflozin 5mg qd or Placebo 5mg qd

11.4 Cautions for the prior and concomitant medications

- ① All study patients will receive ertugliflozin or placebo in addition to their usual prior medications. They will receive optimal medical treatment for their underlying disease such as hypertension, diabetes, arrhythmia and/or coronary artery disease.
- 2 Any therapy started or stopped after randomization will be regarded as concomitant medications. All study patients will be educated to inform their concomitant therapy to the investigator before they start.
- 3 Hypoglycemia-associated agents, guanethidine, direct acting antiviral agents (HCV), alpha-lipoic acid, selective serotonin reuptake inhibitors, salicylates, prothionamide, pegvisomant, ,monoamine oxidase inhibitors, maitake, androgens (exceptions: danazol) may enhance the hypoglycemic effect of SGLT2 inhibitor.
- SGLT2 Inhibitors may enhance the hypoglycemic effect of Insulins and sulfonylureas. Consider a decrease in insulin and sulfonylurea dose when initiating therapy with a sodium-glucose cotransporter 2 inhibitor and monitor patients for hypoglycemia.

11.5 Blinding and Unblinding Method

Investigational product will be administered in a double-blinded fashion. The identity of the treatment will be concealed by the use of study drugs that are identical in packaging, labeling, appearance and odor. Access to the randomization schedule and treatment codes will be maintained through the IWRS. Routines for this will be described in the IWRS user manual that will be provided to each site. All echo studies will be analyzed by core laboratory persons who will be blinded to treatment assignment. Patients and investigators will remain blind to the identity of treatment from the time of randomization until database lock. Treatment codes will not be broken

for the planned analyses of data until all decisions on the evaluability of the data from each individual patient have been made and documented.

In order to assure subject's safety, the study blind may be broken in emergency for the following reason:

- 1) in the opinion of the Medical Monitor and/or the PI, it is in the patient's best interest to do so
- 2) knowledge of the treatment will alter the clinical management of the patient

In the case of an emergency that requires unblinding, the Investigator can enter IWRS to unblind the patient without prior contact with the Medical Monitor although follow-up between the Investigator and Medical Monitor must occur so that all parties are aware of the unblinding. A series of questions must be answered to ensure that the Investigator does not accidently unblind a patient. Although it is recommended that the Investigator contact the Medical Monitor prior to unblinding any patient, in instances where this is not feasible or advisable the PI directly access the patient's treatment assignment using the IWRS. The emergency contact telephone number will be provided for each Medical Monitor.

12 Protocol Procedures

